6.14.2.2. Common Adverse Events

The percentage of subjects with TEAEs will be summarized by treatment using MedDRA PT for the common TEAEs (occurred in $\geq 5\%$ of subjects [before rounding] of any treatment group). Events will be ordered by decreasing frequency in the total LY treatment group. The summary will be presented for Safety Population Period 1.

6.14.2.3. Deaths, Other Serious Adverse Events, and Other Significant Adverse Events

A listing of all deaths will be provided.

The number and percentage of subjects who experienced an SAE (including deaths) during the treatment period will be summarized by treatment using MedDRA PT nested within SOC. Events will be ordered by decreasing frequency in the total LY treatment group within SOC. The summaries will be presented for Safety Population Period 1, Safety Population Period 2, Safety Population All SC LY, and Safety Population All LY.

The number and percentage of subjects who permanently discontinued from study treatment due to an AE (including AEs that led to death) during the treatment period will be summarized by treatment using MedDRA PT nested within SOC. Events will be ordered by decreasing frequency in the total LY treatment group within SOC. The summaries will be presented for Safety Population Period 1, Safety Population Period 2, Safety Population All SC LY, and Safety Population All LY.

6.14.3. Clinical Laboratory Evaluation

Summaries will be provided in both International System of Units (SI) and US conventional units (when different). Normal limits from the performing lab will be used to define low and high.

Some of the analyses below may be incorporated into interactive display tools instead of or in addition to a static display. As such, the box plots for changes from baseline and the shifts to low/high summaries will be presented in a static display; the box plots for observed values, scatter plots and shift tables will be reviewed, if necessary, as an interactive display.

The following will be conducted for laboratory analyte measurements collected quantitatively:

- Box plots for observed values: Values at each visit (starting at randomization) will be displayed in box plots for subjects who have both a baseline and a result for the specified visit. Unplanned measurements will be excluded. Baseline will be the last non-missing observation in the baseline period. Original-scale data will be used for the display. These box plots will be used to evaluate trends over time and to assess a potential impact of outliers on central tendency summaries.
- Box plots for change values: Change from baseline to each visit will be displayed in box plots for subjects who have both a baseline and a result for the specified visit. Change from baseline to last observation will also be summarized and analyzed for subjects who have both baseline and at least 1 postbaseline result. Baseline will be the last non-missing observation in the baseline period. The last non-missing observation in the treatment period will be used as the last observation. Unplanned measurements will be excluded. The change from baseline to last observation will be summarized within the box plot of changes (rightmost column), and descriptive summary statistics will be included in a table below the box plot.

- Outlier/shift displays focusing on low values: A scatter plot, a shift table, and a shift to low table will be created. Unplanned measurements will be included. The scatter plot will plot the minimum value during the baseline period versus the minimum value during the treatment period. The shift table will include the number and percentage of subjects within each baseline category (minimum value is low, normal, high, or missing) versus each postbaseline category (minimum value is low, normal, high, or missing) by treatment. Subjects in the Safety Population will be included in the shift table. The shift from normal/high to low table will include the number and percentage of subjects by treatment whose minimum baseline result is normal or high and whose minimum treatment result is low. Subjects whose minimum baseline result is normal or high and have at least one result during the treatment period are included. The Fisher's exact test will be used to compare percentages of subjects who shift from normal/high to low between all Period 1 LY dose regimens (200 mg IV, 600 mg IV, 1000 mg IV) combined and placebo for Safety Population Period 1.
- Outlier/shift displays focusing on high values: The same approach described for low values will be used, except maximum values will replace minimum values.

Box plots will be displayed for Safety Population Period 1. Spaghetti plots will be explored to evaluate individual subject trends over time across the whole study. The summary of treatment-emergent abnormal, high, or low laboratory results at any time will be provided for Safety Population Period 1, Safety Population Period 2, Safety Population All SC LY, and Safety Population All LY.

For laboratory analyte measurements, a listing of abnormal findings will be created. The listing will include subject ID, treatment group, laboratory collection date, analyte name, and analyte finding.

6.14.4. Vital Signs and Physical Characteristics

As described in Section 6.14.3, some of the analyses below may be incorporated into interactive display tools instead of or in addition to a static display. As such, the box plots for changes from baseline and the shifts to low/high summaries will be presented in a static display; the box plots for observed values, scatter plots and shift tables will be reviewed, if necessary, as an interactive display.

The following will be conducted for vital signs and physical characteristics (systolic blood pressure [BP], diastolic BP, pulse, weight, BMI):

- Box plots for observed values: To be created as described in Section 6.14.3 for laboratory analyte measurements.
- Box plots for change values: To be created as described in Section 6.14.3 for laboratory analyte measurements.
- Outlier/shift displays focusing on low values: To be created as described in Section 6.14.3 for laboratory analyte measurements, except the definition of treatment-emergent includes a threshold for change in addition to a limit as described in [Table AMAG.6.12](#). A treatment-emergent low result is defined as a change from a value

greater than or equal to the low limit at all baseline visits to a value less than the low limit at any time that meets the specified change criteria during the treatment period. The denominator will be subjects whose values are greater than or equal to the low limit at all baseline visits. To assess decreases, change from the minimum value during the baseline period to the minimum value during the treatment period will be used.

- Outlier/shift displays focusing on high values: The same approach described for low values will be used, except to assess increases, maximum values will replace minimum values. High limits will replace low limits.

Box plots will be displayed for Safety Population Period 1. Spaghetti plots will be explored to evaluate individual subject trends over time across the whole study. The summary of treatment-emergent high or low vital signs results at any time will be provided for Safety Population Period 1, Safety Population Period 2, Safety Population All SC LY, and Safety Population All LY.

Table AMAG.6.12. Categorical Criteria for Abnormal Treatment-Emergent Blood Pressure and Pulse Measurement, and Categorical Criteria for Weight and Changes for Adults

Parameter	Low	High
Systolic BP (mm Hg)	≤ 90 and decrease from baseline ≥ 20	≥ 140 and increase from baseline ≥ 20
Diastolic BP (mm Hg)	≤ 50 and decrease from baseline ≥ 10	≥ 90 and increase from baseline ≥ 10
Pulse (bpm)	< 50 and decrease from baseline ≥ 15	> 100 and increase from baseline ≥ 15
Weight (kg)	(Loss) decrease $\geq 7\%$	(Gain) increase $\geq 7\%$

Abbreviation: BP = blood pressure.

6.14.5. Electrocardiograms

Complete electrocardiogram (ECG) data will not be part of the clinical database for this study. Per protocol, any clinically significant findings from ECGs that result in a diagnosis and that occur after the subject receives the first dose of the investigational treatment will be reported to Lilly or its designee as an AE via electronic case report form (eCRF).

[figure not shown]
6.14.6. Immunogenicity

Figure AMAG.6.1 provides an overview of the immunogenicity assay process.

At a high level, an individual sample is potentially examined multiple times in a hierarchical procedure to produce a sample anti-drug antibodies (ADA) assay result and potentially a sample neutralizing antibody (NAb) assay result. The cut points used, the drug tolerance of an assay, and the possible values of titers are operating characteristics of the assay, which will be study specific.

It can be the case that the presence of high concentrations of LY will affect the measurements of the presence of ADA or NAb, and conversely high levels of ADA or NAb may affect the measurement of LY concentration. Thus, an LY drug concentration, assessed from a sample drawn at the same time as the ADA sample, plays a key role in clinical interpretation of a sample when the laboratory result is Not Detected, as shown in Figure AMAG.6.1.

The rest of this section defines the component concepts of Figure AMAG.6.1 in greater detail.

Abbreviations: ADA = anti-drug antibodies; NAb = neutralizing antibody; PK = pharmacokinetics.

Figure AMAG.6.1. Flow chart of ADA sample assessment with clinical interpretation.

6.14.6.1. Definitions of Sample ADA Status

Table AMAG.6.13. Sample ADA Assay Results

Sample Laboratory Result	Explanation
Detected	ADA are detected and confirmed.
Not Detected	The raw result as reported from the laboratory indicates Not Detected. The clinical interpretation of such results depends on other factors (see below).
No Test, QNS, etc.	Sample exists but was unevaluable by the assay.

Abbreviations: ADA = anti-drug antibodies; QNS = quantity not sufficient.

Table AMAG.6.14. Sample Clinical ADA Interpretation Results

Sample Clinical Interpretation	Explanation
ADA Present	ADA assay result is Detected.
ADA Not Present	ADA assay result is Not Detected and simultaneous drug concentration is at a level that has been demonstrated to not interfere in the ADA detection method (ie, drug concentration is below the assay's drug tolerance level). If drug concentration is not available for a treatment-period sample, the sample is inconclusive (see below). For subjects receiving placebo, drug concentration is not assessed and is assumed to be below the assay's drug tolerance level.
ADA Inconclusive	ADA assay result is Not Detected but drug concentration in the sample is at a level that can cause interference in the ADA detection method, or drug concentration is planned per protocol but is not available.
ADA Not Detected with Drug Concentration Not Available	If drug concentration analysis was planned but result is not available for a treatment-period sample, a Not Detected sample will be declared ADA Not Detected with Drug Concentration Not Available. In the computation of Subject ADA status (see below, Section 6.14.6.3), these samples will be considered ADA Not Present, on the basis of prior knowledge that the drug tolerance level of the ADA assay is high relative to the expected drug concentration levels.
ADA Missing	ADA sample not drawn, QNS, not tested, etc, causing there to be no laboratory result reported or the result is reported as No Test.

Abbreviations: ADA = anti-drug antibodies; QNS = quantity not sufficient.

Parallel terminology applies for NAb Detected, NAb Not Detected, NAb Present, NAb Not Present, NAb Inconclusive, NAb Not Detected with Drug Concentration Not Available, and NAb Missing. ADA and NAb are distinct assays and have different assay operating characteristics.

6.14.6.2. Definitions of Immunogenicity Assessment Periods

Immunogenicity Baseline Observations: Baseline period for immunogenicity assessment for each subject includes all observations on or prior to the date of the first administration of study drug (whether LY3074828 or comparator). In instances where multiple baseline observations are collected, the last non-missing value prior to study drug is used as baseline. For studies

where applicable, subjects who receive LY3074828 subsequent to receiving Placebo, the original pre-Placebo baseline value is used.

Immunogenicity Postbaseline Period Observations: Postbaseline period observations for each subject include all observations after the first administration of study drug. As mentioned in the previous section, for subjects who receive LY3074828 subsequent to receiving Placebo, the baseline is the original pre-Placebo baseline. However, the analysis uses only the postbaseline observations after receiving LY3074828.

6.14.6.3. Definitions of Subject ADA Status

Subject evaluable for treatment-emergent ADA: A subject is evaluable for treatment-emergent ADA if the subject has a non-missing baseline ADA result, and at least 1 non-missing postbaseline ADA result.

Treatment-emergent ADA positive (TE ADA+) subject: A subject who is evaluable for treatment-emergent ADA is TE ADA+ if either of the following holds:

- a. The subject has baseline status of ADA Not Present and at least 1 postbaseline status of ADA Present with titer ≥ 2 * minimum required dilution (MRD) of the ADA assay (Treatment Induced).
- b. The subject has baseline and postbaseline status of ADA Present, with the postbaseline titer being 2 dilutions (4-fold) greater than the baseline titer. That is, the subject has baseline status of ADA Present, with titer 1:B, and at least 1 postbaseline status of ADA Present, with titer 1:P, with $P/B \geq 4$ (Treatment Boosted).

Treatment-emergent ADA Inconclusive subject: A subject who is evaluable for TE ADA is TE ADA Inconclusive if $\geq 20\%$ of the subject's postbaseline samples, drawn pre-dose, are ADA Inconclusive and the subject is not otherwise ADA+.

Treatment-emergent ADA negative (TE ADA-) subject: A subject who is evaluable for TE ADA is TE ADA- when the subject is not TE ADA+ and the subject is not TE ADA Inconclusive.

6.14.6.4. Analyses to Be Performed

Analyses will be performed for Safety Population Period 1 and Safety Population All LY (see Section 6.1.2).

A listing will be provided of all immunogenicity assessments for those subjects who at any time had ADA Present. This includes the laboratory ADA assay result (Detected or Not Detected), LY concentration from a simultaneous PK sample, and the clinical interpretation result that combines these (ADA Present, ADA Not Present, ADA Inconclusive, Missing). When detected, a titer will be included, and TE ADA+ observations will be flagged. Also included will be the laboratory NAb assay result (Detected or Not Detected) and the NAb clinical interpretation result (NAb Present, NAb Not Present, NAb Inconclusive, Missing) when the NAb assay was performed.

For the remainder of this section, “ADA result” will refer to the clinical interpretation result. “NAb result” will be handled similarly.

The number and proportion of subjects who are TE ADA+ will be tabulated by treatment group, where proportions are relative to the number of subjects who are TE ADA evaluable, as defined above. The tabulation will include all postbaseline observations, the number and proportion of subjects with ADA Present at baseline, and the number and proportion of TE ADA+ subjects exhibiting NAb+.

For each TE ADA+ subject, a plot will be constructed of titer values from individual samples over time. Samples that are ADA Not Present or ADA Inconclusive will also be indicated.

A summary will be provided of the number and percentage of LY-treated subjects experiencing TEAEs (overall and by PT) by subject TE ADA status (TE ADA+, TE ADA-, TE ADA Inconclusive). The PT will be ordered by decreasing incidence in TE ADA+ status group.

A listing will be provided that includes any subject who has ADA Detected at any time, OR who reports specific TEAEs (see [Table AMAG.6.15](#)). This listing includes a time course of ADA (clinical interpretation result plus flags for samples meeting TE ADA+ criteria and for NAb+ samples) along with the AE.

Table AMAG.6.15. TEAEs for Listing with ADA/NAb Results

Events satisfying Anaphylaxis SMQ (narrow or broad)
 Events satisfying Hypersensitivity SMQ (narrow or broad)
 Events satisfying Angioedema SMQ (narrow or broad)
 Events mapping to HLT of Injection site reaction
 Events mapping to HLT of Infusion site reaction
 Events mapping to HLT of Administration site reaction

Abbreviations: ADA = anti-drug antibodies; HLT = high level term; MedDRA = Medical Dictionary for Regulatory Activities; NAb = neutralizing antibody; SMQ = standardized MedDRA query; TEAE = treatment-emergent adverse event.

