- Period 3 (Weeks 52 to 104): All subjects having clinical benefit per investigator and continuing on study treatment may proceed to Period 3 and receive 300 mg SC LY3074828 Q4W open-label starting at Week 52 through Week 104. Patients not receiving clinical benefit at Week 52 will discontinue treatment and will enter the Follow-Up period.
- Follow-Up (Weeks 104 to 120): At Week 104, subjects will stop treatment and be followed for safety for an additional 16 weeks.
- [Figure AMAG.1](#) illustrates the study design.

Abbreviations: IV = intravenous; Q4W = every 4 weeks; SC = subcutaneous; SES-CD = Simple Endoscopic Score for Crohn’s Disease.
 *Subjects who have not had any improvement in SES-CD score from baseline at Week 12, as determined by the central reader, will receive IV LY3074828 1000 mg + SC placebo.

Figure AMAG.1. Illustration of study design for Clinical Protocol I6T-MC-AMAG.

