7.8.2. Special Treatment Considerations

7.8.2.1. Premedication for Infusions

Premedication for the infusions is not planned. However, if an infusion reaction occurs, appropriate medication may be used as determined by the study investigators.

Any premedication given will be documented as a concomitant therapy.

7.8.2.2. Management of Hypersensitivity Events, Fever Associated Reactions, and Infusion/Injection Site Reactions

During and after study drug administration, patients should be closely monitored for signs or symptoms of AEs, including hypersensitivity events, other fever associated reactions and infusion or injection site reactions.

Systemic Hypersensitivity Events

If a patient experiences a systemic hypersensitivity event involving the skin or mucous membranes, respiratory, cardiovascular, gastrointestinal, or urinary systems, during or up to 6 hours after an infusion of study drug, the following guidance should be followed (see [Appendix 6](#) for additional information):

- Study drug infusion should be stopped immediately and appropriate supportive care provided according to local standard practice (for example, administration of epinephrine, anti-histamine, systemic steroids, and/or bronchodilators).

- After the patient's stabilization, additional immunogenicity, PK, and hypersensitivity markers samples should be collected as follows:
 - As soon as possible after the event occurs
 - 4 weeks after the event
 - 12 weeks after the event
- The patient should continue to be monitored until resolution or stabilization of the symptoms, as clinically appropriate.
- Permanently discontinue the study drug after a systemic drug administration reaction.
- If the patient discontinues study drug but remains in the study, management should follow as outlined in Section 8.1.1, and immunogenicity, PK, and hypersensitivity markers should be collected at 4 and 12 weeks after the event.
- If the patient discontinues participation in the study, the patient should proceed to early termination procedures. The patient will need to return after early termination procedures for 4 and 12 week immunogenicity, PK, and hypersensitivity markers collections.
- The medical monitor should be notified as soon as feasible.

Fever-Associated Reactions

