If a patient experiences a fever-associated reaction consisting of headache, rigors and/or temperature $>38^{\circ}\text{C}$ (in the absence of signs or symptoms of a systemic hypersensitivity event) during or up to 6 hours after an infusion of study drug, the following guidance should be followed:

- Study drug infusion should be interrupted and appropriate medical care should be administered (for example, nonsteroidal anti-inflammatory drugs [NSAIDs], antipyretics or antihistamines).
- Additional immunogenicity, PK, and hypersensitivity markers samples should be collected as follows:
 - As soon as possible after the event occurs
 - 4 weeks after the event
 - 12 weeks after the event
- Resumption of study drug infusion after interruption, possibly at a slower rate of administration, can be considered if symptoms resolve and it is deemed to be medically appropriate based on the investigator's discretion, and considering the risk/benefit of readministration.
- Patient should remain in observation, as is clinically appropriate for the patient's symptoms.
- Premedication prior to subsequent study drug administration may be considered, if judged by the investigator to be appropriate for the individual patient.
- If the patient discontinues study drug but remain in the study, management should follow as outlined in Section 8.1.1, and immunogenicity, PK, and hypersensitivity markers should be collected at 4 and 12 weeks after the event.

- If the patient discontinues from the study early for any reason, they should return to complete 4 and 12 week follow-up immunogenicity, PK, and hypersensitivity markers collections.
- If the patient develops systemic hypersensitivity symptoms or signs, they should be managed as described above for a systemic hypersensitivity event.

Infusion Site Reactions

If a patient experiences an infusion site reaction, including urticaria, pruritus, or angioedema localized to the IV infusion site (in the absence of systemic hypersensitivity signs or symptoms), during or up to 6 hours after an infusion of study drug, the following guidance should be followed:

- Study drug infusion should be interrupted and appropriate medical care should be administered (for example, NSAIDS, anti-pyretics or antihistamines).
- Additional immunogenicity, PK, and hypersensitivity markers samples should be collected as follows:
 - As soon as possible after the event occurs
 - 4 weeks after the event
 - 12 weeks after the event

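### In Safety Population All LY, adverse events are compared by an ever-positive ADA label with no allowance for unequal follow-up, so the comparison is biased in a direction that depends on the event

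*SAP*

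**What the plan says.** **Status.** Under SAP 6.14.6.3 an evaluable subject who is ADA-negative at baseline becomes TE ADA+ with "at least 1 postbaseline status of ADA Present with titer" at or above twice the minimum required dilution. A subject already positive at baseline needs a four-fold rise. One sample is enough, and the label then belongs to the subject, not to a time.

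**Samples that count.** SAP 6.14.6.2 says: "Postbaseline period observations for each subject include all observations after the first administration of study drug". For subjects who had placebo first, only samples after LY3074828 (LY) count. No end date is given and there is no limit to scheduled draws. A pre-dose condition appears in 6.14.6.3, but only for the inconclusive category: "postbaseline samples, drawn pre-dose, are ADA Inconclusive".

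**The table.** SAP 6.14.6.4 specifies: "A summary will be provided of the number and percentage of LY-treated subjects experiencing TEAEs (overall and by PT) by subject TE ADA status". It is planned for Safety Population Period 1 and Safety Population All LY.

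**Follow-up in All LY.** Protocol 5.1 states: "Patients not receiving clinical benefit at Week 52 will discontinue treatment and will enter the Follow-Up period". Others continue to Week 104 and then 16 further weeks. Placebo subjects start LY about 12 weeks later, and some subjects terminate early. In SAP Table AMAG.6.4 the All LY (a) event window closes at the last LY dosing visit, while All LY (b) runs to Week 120.

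**Extra samples.** After a systemic hypersensitivity event, Protocol 7.8.2.2 says "additional immunogenicity, PK, and hypersensitivity markers samples should be collected as follows": as soon as possible, then 4 and 12 weeks after the event. The same applies to fever-associated and infusion site reactions. Protocol amendment (b) added these samples. The SAP revision history says it reflects amendment (a), and the SAP is silent on them.

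**The concern.** A crude percentage with an event rises with time observed, and so does the chance of at least one positive sample. If observation time varies, longer-followed subjects collect in the TE ADA+ column and bring more events with them, even when antibody and event are unrelated. In All LY (a) the two clocks also differ: a follow-up sample can reclassify a subject whose counted events all happened earlier.

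The opposite can happen as well. If a reaction ends participation, the subject has less time left to turn positive, so events collect among those who are not TE ADA+.

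At stake is the exploratory objective on how antibodies affect safety (Protocol section 4; SAP Table AMAG.4.1), and the comparison of antibody-positive and antibody-negative subjects described in Protocol 10.3.4. No primary or secondary efficacy conclusion depends on it.

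**Working it through.** The documents give no figure for this table, and no ADA incidence, event rate or dropout rate. The rates below are therefore assumptions. The visit times and the 16-week follow-up come from the protocol.

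**1. Formula.** Let group *i* have share w and follow-up T weeks, with independent constant hazards a (antibody) and l (event):

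- P_A = 1 − exp(−aT) and P_E = 1 − exp(−lT)
- percent with event among TE ADA+ = Σ w·P_A·P_E / Σ w·P_A
- percent with event among the rest = Σ w·(1 − P_A)·P_E / Σ w·(1 − P_A)

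If all T are equal, both lines reduce to P_E and the ratio is 1. Unequal T is what creates the false link.

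**2. Worked example.** Assume 52-week incidence of 30% for antibody and 20% for one event type. Then a = −ln(0.70)/52 = 0.00686 and l = −ln(0.80)/52 = 0.00429 per week. Assume 10% leave in Period 1, 20% in Period 2 and 25% stop at Week 52; the other 45% complete. Midpoints are used for the first two groups, and 52 + 16 = 68 weeks for the third.

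| Group | w | T | P_A | P_E |
|---|---|---|---|---|
| Leaves in Period 1 | 10% | 6 | 4.0% | 2.5% |
| Leaves in Period 2 | 20% | 32 | 19.7% | 12.8% |
| Stops at Week 52 | 25% | 68 | 37.3% | 25.3% |
| Completes | 45% | 120 | 56.1% | 40.2% |

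- Σ w·P_A = 0.389; Σ w·P_A·P_E = 0.1303; Σ w·P_E = 0.2726
- TE ADA+: 0.1303 / 0.389 = 33.5%
- rest: (0.2726 − 0.1303) / (1 − 0.389) = 23.3%
- ratio: 33.5 / 23.3 = 1.44

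A simulation of 1,000,000 subjects at the same assumed rates, with antibody detected only at the scheduled immunogenicity visits, gave 33.5% against 23.2%, ratio 1.44.

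**3. Range, no true link in any row.** Assumed 52-week ADA incidence was 10% or 30%, and event incidence 5%, 20% or 40%. Assumed exits in Period 1 / in Period 2 / at Week 52 were 5/10/15%, 10/20/25% or 15/25/30%. The later LY start of placebo subjects was not modelled.

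| Setting | Crude ratio |
|---|---|
| Period 1, equal follow-up, scheduled samples | 0.96 to 1.01 |
| Period 1, 10% dropout, scheduled samples | 1.00 to 1.06 |
| All LY, equal 120 weeks | 1.00 to 1.01 |
| All LY, unequal follow-up, constant hazards | 1.14 to 1.60 |
| All LY, unequal follow-up, antibody and events both early | 1.11 to 1.16 |
| Equal 120 weeks plus event-triggered samples | 1.00 to 1.08 |
| 12-week window plus event-triggered samples | 1.23 to 1.47 |
| All LY, event ends participation, with triggered samples | 0.79 to 0.94 |
| All LY, event ends participation, without them | 0.62 to 0.79 |

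The 12-week triggered-sample row is an upper bound: it lets the 4- and 12-week samples reach past the window for subjects with events only. A repeat simulation on the protocol sampling visits gave 1.26 to 1.63 for All LY with constant hazards and 1.09 to 1.22 with early clustering.

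**4. Does person-time repair it?** With constant hazards, a rate ratio using ADA status at the time of the event returns 0.99 to 1.01. If antibody and events both cluster early, plain person-time overcorrects, to 0.59 to 0.66 (0.64 to 0.67 in the repeat run), because early high-risk time is mostly antibody-free. Stratifying person-time by time since first LY dose restores 0.99 to 1.01.

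**The case against.** Several points on the other side stand.

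- The All LY analyses are descriptive (SAP 6.14) and the objective is exploratory. No test or decision rule uses this table.
- The SAP lists the ADA time course beside the event for anyone with antibody detected or a Table AMAG.6.15 event, and plots titers for each TE ADA+ subject. With about 180 randomized subjects, order can be read case by case.
- SAP 6.14 allows exposure-adjusted rates.
- The size rests on assumed rates.

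These soften the point without removing it. A listing is not a comparison, and the exposure-adjusted rates are optional and not tied to ADA status.

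A reader might infer more than the documents support:

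- **That a false positive link is expected for every event.** A systemic reaction ends dosing under Protocol 7.8.2.2. The subject may stay in the study (8.1.1), but where the event ends participation the ratio falls below 1.
- **That ignoring order creates the link.** With equal 120-week follow-up, 48% to 61% of events in TE ADA+ subjects preceded the first positive sample, yet the ratio was 1.00 to 1.01. Order affects attribution; by itself it does not shift the ratio when nothing is going on.
- **That event-triggered samples drive it.** They follow only certain reactions during or within 6 hours of an infusion, while the table covers all TEAEs. Over 120 weeks they add little. They could matter in a 12-week window.
- **That only a whole-study comparison is planned.** Period 1 is tabulated too, although the SAP does not say whether later samples can set Period 1 status.

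**Conclusion.** The point holds for Safety Population All LY. With no true link, the planned percentages would give a ratio of about 1.1 to 1.6 for events that do not end follow-up, and possibly below 1 for reactions that end participation. A ratio above 1 is therefore not evidence of an antibody effect, and a ratio near 1 does not exclude one. These sizes depend on assumed ADA incidence, event rates and dropout, which the documents do not supply. The mechanism itself needs only unequal follow-up and an ever-positive label, and both are in the text. The Period 1 table is nearly unbiased if status comes from scheduled samples within Period 1. Because the analysis is exploratory and descriptive, this is a cheap improvement and not a threat to the trial's main conclusions.

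**What to change.** In SAP 6.14.6.4, for the Table AMAG.6.15 event groups in Safety Population All LY, add a summary of first events per 100 patient-years by ADA status at event onset:

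- Use two states: before or without TE ADA+, and on or after the first TE ADA+ sample.
- Stratify by time since first LY dose, for example 0–4, 4–12, 12–24, 24–52 and more than 52 weeks. Unstratified person-time should not be used alone, for the reason in step 4.
- Derive status for this summary from scheduled samples only. Keep event-triggered samples in the listing and in overall ADA incidence.

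For the Period 1 table, state that status uses only scheduled samples up to the Period 1 end date.

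The cost is SAP wording and one added table. It needs sample and event dates for all LY-treated subjects, including those outside the existing listing. Some strata will be sparse, and an antibody seen only in an event-triggered sample will not count as positive in this one summary.
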